15.7 Exploratory Objectives

This study has 3 exploratory objectives: (1) To assess the relationship between migration and serum CCL3, (2) To assess the relationship between pp65-specific polyfunctional CD8+ T cells and migration, and (3) To assess the relationship between pp65-specific polyfunctional CD8+ T cells and serum levels of CCL3.

15.7.1 Exploratory Objective #1: Migration and CCL3

Objective	To assess the relationship between serum CCL3 levels and increased DC migration.
Analysis Set	All patients who undergo migration studies who have CCL3 levels measured.
Outcome	Correlation coefficient between fold change of CCL3 and migration.
Hypothesis	We hypothesize that fold change in CCL3 will be highly correlated with increased migration.

Analysis Plan	A Spearman rank correlation coefficient will assess the association between CCL3 change from pre to post-vaccine 4, and migration.
Additional Analyses	As an additional exploratory analysis of CCL3, a one-sample t-test or a Wilcoxon rank sum test will assess whether fold change in CCL3 between pre- and post-Td pre-conditioning differs from 0.

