9.3 Rationale for Correlative Studies

Please see Section 12.7.4 ¹¹¹Indium-labeling of Cells for *in vivo* Trafficking Studies. PLEASE NOTE: With approval of Protocol v.20220204, this correlative study will no longer be conducted.

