10 STUDY DRUG

10.1 Names, Classification, and Mechanism of Action

Tetanus-Diphtheria Toxoid (Td Toxoid adsorbed)

Td is indicated for active booster immunization against tetanus, diphtheria, and pertussis as a single dose; substitute 1-time dose of Tdap for Td booster, then standardly boost with Td every 10 years. Please refer to Section 9.1 on the use of Td in this protocol.

DC Vaccine

Human CMV pp65-LAMP mRNA-pulsed autologous DCs with GM-CSF is the name of the study drug given with every vaccine. This vaccination will then consist of administration of 2×10^7 CMV pp65-LAMP mRNA loaded mature DCs as described above. In up to 16 patients, the fourth vaccine will be labeled with ¹¹¹In (50 μ Ci / 5×10^7 DCs) (Nycomed-Amersham, Chicago, IL) prior to injection. The class of action for all study drugs is a biological with the exception of the tetanus toxoid, which is an antitoxin.

GM-CSF (LEUKINE®; Sargramostim)

GM-CSF will be obtained from commercial supply and stored in the ICS, as a sterile, white, preservative-free powder lyophilized powder in a vial containing 250 mcg to be reconstituted in 0.5 mL of sterile water for injection.

Leukapheresis and Dendritic Cell Vaccine Generation

At least two leukaphereses may be performed on each patient enrolled on this protocol. The leukapheresis will be used for DC generation and immunologic monitoring. If the subjects were part of the companion study (Pro00102797) and have already undergone the leukapheresis procedure the DCs from that study will be used for the current study and any unused vaccine products will be handled as indicated by the patient in the companion study. All leukaphereses will be approximately a 4-hour leukapheresis. It is estimated that 10-12 L of blood will be processed during this leukapheresis. An additional 4-hour leukapheresis will be requested from patients with positive immunological responses to the therapy for additional immunologic monitoring studies or for patients who need additional DCs generated to ensure a total of 10 vaccines.

DCs will be generated from the first leukapheresis *in vitro* by 7-day culture with GM-CSF and IL-4. Peripheral blood mononuclear cells (PBMC) for *in vitro* generation of DCs will be obtained by leukapheresis at the Duke Apheresis Unit and transported to the Cell Processing facility. For patients without sufficient venous access for leukapheresis a temporary intravenous catheter may be inserted.

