15.2 Analysis Sets

All patients who initiate dose-intensified TMZ after completion of standard of care RT and TMZ will be included in the primary efficacy analyses, and toxicity summaries.

Subject to the availability of data, analyses of correlative objectives will include all or some of the patients who undergo vaccine 4. For analyses of migration, the first 16 patients who reach vaccine 4 will undergo migration analyses. For CCL3, all patients who reach vaccine 4 will be included in statistical analyses. For analyses of polyfunctionality, the first 24 patients who reach vaccine 4 will be considered.

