15.7.2 Exploratory Objective #2: Polyfunctionality and Migration

Objective	To assess the relationship between pp65-specific polyfunctional CD8+ T cells and DC migration.
Analysis Set	All patients who undergo migration studies who have polyfunctional levels measured.
Outcome	Correlation coefficient between fold change in polyfunctionality and migration
Hypothesis	We hypothesize that increased pp65-specific polyfunctionality CD8+ T cells will be highly correlated with increased DC migration.
Analysis Plan	A Spearman rank correlation coefficient will assess the association between fold change in polyfunctionality and migration.

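### After the migration study was discontinued, Section 15.7.1 still places the only test of CCL3 change across Td under a migration-patient analysis set, in conflict with Section 15.2

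*Combined protocol and SAP*

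**What the plan says.** **The test.** Section 15.7.1 (Exploratory Objective #1) has one Analysis Set row: "All patients who undergo migration studies who have CCL3 levels measured". Its Additional Analyses row adds that "a one-sample t-test or a Wilcoxon rank sum test will assess whether fold change in CCL3 between pre- and post-Td pre-conditioning differs from 0". No other section specifies a test of CCL3 change across Td. Table 1 lists the mean fold change in CCL3 as an endpoint separate from its correlation with migration, states no population for it, and refers to Section 15.7.1.

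**The general rule.** Section 15.2 says "For CCL3, all patients who reach vaccine 4 will be included in statistical analyses". It also says that "the first 16 patients who reach vaccine 4 will undergo migration analyses".

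**The discontinuation.** Section 9.3 states "With approval of Protocol v.20220204, this correlative study will no longer be conducted". Section 7.1 (Study Agent), the secondary migration row of Table 1 and Section 15.6.1 carry matching notes. No such note appears in the exploratory rows of Table 1, in 15.7, 15.7.1 or 15.7.2, or in 15.2. Section 15.7.2 still defines its set as "All patients who undergo migration studies who have polyfunctional levels measured", and Section 10.1 still reads "In up to 16 patients, the fourth vaccine will be labeled with" the isotope.

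**The samples.** Table 4 (footnotes 6 and 8) and Section 12.7.5 schedule serum before Td at the pre-conditioning visit and again at vaccine 4, with no restriction to a subset. Section 15.6.2 anticipates 40 patients with CCL3 at vaccine 4.

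**The concern.** The CCL3 comparison before and after Td needs only two serum samples, and both are planned for every patient who gets that far. Yet it sits inside a migration objective, and the only analysis set in that table depends on a procedure the trial no longer performs. An analyst could defend about 40 pairs (15.2), at most 16 (15.7.1), or not running the test at all, and could choose after seeing the data. A pre-specified analysis set exists to prevent that.

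Two further gaps come from the same amendment. The migration correlations in 15.7.1 and 15.7.2 remain listed as objectives although no new migration data will arise, so they cannot be run as planned. Sections 15.2 and 10.1 still describe migration and labelling work in up to 16 patients.

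**Working it through.** **1. The plan's own CCL3 figure.** The test across Td has no stated sample size, alpha or power. The only sized CCL3 analysis is the Cox model in 15.6.2: SD 12.9, HR 0.95 per unit, two-sided alpha 0.0167, 80% power, 24 deaths.

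- Formula: D = (z(1−α/2) + z(power))² / (SD² × ln(HR)²)
- Numerator: (2.393 + 0.842)² = 10.46
- Denominator: 12.9² × (ln 0.95)² = 166.41 × 0.002631 = 0.4378
- D = 10.46 / 0.4378 = 23.9, rounded up to 24.

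The stated figure reproduces. That analysis uses all patients who reach vaccine 4 and is not in question.

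**2. The candidate analysis sets for the test across Td.**

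| Source | Set | Size |
|---|---|---|
| 15.7.1, Analysis Set row | Migration-study patients with CCL3 | 0 to 16; number imaged not given |
| 15.2 | All who reach vaccine 4 | about 40 (15.6.2) |
| Table 1 | No population stated | refers to 15.7.1 |
| Table 4, 12.7.5 | Both samples, no subset | all who reach vaccine 4 |

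**3. Precision.** The 95% CI half-width, in SD units of the paired change, is t(0.975, n−1)/√n.

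- n = 16: 2.131/4 = 0.533
- n = 40: 2.023/6.325 = 0.320

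**4. Power.** One-sample t-test, noncentral t with noncentrality d√n, where d is the true change in SD units. Two-sided 0.05 and the values of d are assumptions, because the plan gives neither. The rows for 4, 8 and 12 patients span part of the possible range of imaged patients.

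| n | CI half-width (SD) | Power, d = 0.3 | Power, d = 0.5 | d for 80% power |
|---|---|---|---|---|
| 4 | 1.59 | 6% | 11% | 2.13 |
| 8 | 0.84 | 11% | 23% | 1.16 |
| 12 | 0.64 | 16% | 35% | 0.89 |
| 16 | 0.53 | 20% | 46% | 0.75 |
| 40 | 0.32 | 46% | 87% | 0.45 |

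The power columns count rejection in the direction of the true change. With n of 0 or 1 no SD can be estimated and the t-test cannot be run.

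**5. The wording of the test.** The null value is given as 0. A fold change expressed as a ratio equals 1 when nothing changes; it is the log ratio that equals 0. The rank sum test compares two independent samples. The one-sample or paired rank test is the signed-rank test, which the plan itself names for the paired comparison in 15.6.3.

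**The case against.** The best defence is that Section 15.2 is where analysis sets are defined, and it puts every patient who reaches vaccine 4 into CCL3 analyses. The disputed row presents itself as an extra exploratory look at CCL3, not as the migration correlation. Table 1 separates the two endpoints and attaches no migration restriction to the CCL3 change. On that reading the test already uses about 40 patients and only tidying remains.

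This defence stands in part. A reader might infer from 15.7.1 that the test is definitely limited to migration patients, so that at least 24 of 40 pairs (40 − 16) are discarded. The documents do not support that: 15.2 says otherwise, the samples are collected regardless, and the wider analysis stays possible. What the defence does not do is settle the conflict. The analysis-specific row names a different population from the general rule, and no rule of precedence is given.

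A reader might also infer that Section 10.1 directs labelling that will actually go ahead. Sections 7.1 and 9.3 state the discontinuation, Table 4 has no imaging row, and 10.1 sets a ceiling that zero patients satisfies. This is leftover text to reconcile.

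Nor is the test the trial's central mechanistic step. Section 7.2 lists CCL3 among several expected effects, next to migration, polyfunctional T cells, PFS and OS. The test is exploratory, has no power statement, and asks only whether the change differs from 0, in either direction.

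**Conclusion.** The point holds as an unresolved conflict between 15.2 and 15.7.1, together with exploratory migration objectives that were not updated when version 20220204 ended the migration study.

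Its size depends on which set is followed. Under 15.7.1 the half-width is at best 0.533/0.320 = 1.67 times that under 15.2, and worse or undefined if few patients were imaged. These figures assume a t-test at two-sided 0.05, assumed effects in SD units, and that all 40 anticipated patients supply both samples; 40 is an expected headcount, not a count of complete pairs.

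The consequence is confined to exploratory results. The primary survival analysis and the remaining secondary analyses do not use this set. The change is still worth making, because it costs little and removes a choice of population that could otherwise be made after seeing the data.

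**What to change.** 1. In 15.7.1, separate the CCL3 comparison before and after Td from the migration objective and give it its own analysis set: all patients with both the pre-Td and the vaccine 4 sample. State the alpha and sidedness, or say that it is estimation only.
2. In the same sentence, test the log fold change against 0 (or the ratio against 1), using a one-sample t-test or a Wilcoxon signed-rank test in place of the rank sum test.
3. In Table 1, 15.7, 15.7.1 and 15.7.2, mark the migration correlations as removed, or limit them to a description of patients imaged before version 20220204, and report how many there were.
4. Reconcile the remaining migration and labelling text in 15.2 and 10.1 with the discontinuation stated in 7.1, 9.3 and 15.6.1.

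The cost is protocol and SAP wording only. Both samples are already scheduled, Section 12.7.5 already plans CCL3 measurement at both visits, and no analysis outside the exploratory section has to change.

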8 OBJECTIVES AND ENDPOINTS

Table 1. Objectives and Endpoints

	Objective	Endpoint	Analysis
Primary	Determine if Td preconditioning of pp65 loaded DC vaccination with GM-CSF extends overall survival.	Median survival from initiation of dose intensive adjuvant temozolamide.	See Section 15.5
Secondary	Assess the association between migration of CMV pp65 RNA-pulsed DCs with GM-CSF to site-draining inguinal lymph nodes after Td pre-conditioning and subsequent survival. (PLEASE NOTE: With Protocol v.20220204, this objective has been removed as it was already addressed in a previous study.)	For survival after vaccine 4, the hazard ratio associated with a 1 unit increase in migration, defined as the maximum percentage of ^{111}In -labeled DCs reaching inguinal nodes during the 48 hours after the 4 th vaccination.	See Section 15.6.1
Secondary	Assess the association between CCL3 measured post-Td pre-conditioning and subsequent survival.	For survival after vaccine 4, the hazard ratio associated with a 1-unit increase in CCL3 measured post-Td pre-conditioning at vaccine 4.	See Section 15.6.2
Secondary	Assess the association between fold changes in T cell polyfunctionality and subsequent survival.	Mean fold change from baseline in the frequency of pp65 antigen-specific CD8 ⁺ T cells producing three or more cytokines (IFN γ , CCL3, IL-2, TNF α , CD107a) at leukapheresis 2 $14 \pm (4)$ days after vaccine 3. Mean fold change from baseline in the frequency of pp65 antigen-specific CD8 ⁺ T cells producing three or more cytokines (IFN γ , CCL3, IL-2, TNF α , CD107a) at vaccine 6. For survival after vaccine 4, the hazard ratio associated with a 1-fold increase in the frequency of pp65 antigen-specific CD8 ⁺ T cells producing three or more cytokines (IFN γ , CCL3, IL-2, TNF α , CD107a).	See Section 15.6.3
Secondary	Assess whether T _{Reg} levels remain low without adjuvant temozolamide.	Maximum mean peak increase from vaccine 1 in percent T _{Reg} of CD4 ⁺ T cells.	See Section 15.6.4
Secondary	Assess the safety of DI-TMZ treatment followed by DC vaccination.	Proportion of patients who experience unacceptable toxicity.	See Section 15.6.5
Exploratory	Assess the association CCL3 levels and migration.	Mean fold change in CCL3 between pre- and post-Td pre-conditioning. Correlation between CCL3 change from fold change in CCL3, and migration.	See Section 15.7.1

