12.7.5 Immunologic Assessments

Immunological response evaluations will be conducted as described in [Table 4](#). All patients will undergo at least 2 leukapheresis procedures – prior to radiation (1 red top 10mL tube) and approximately 2 weeks post vaccine #3 (9 yellow ACD 8.5mL tubes, 2 red top 10mL tubes). If an additional leukapheresis must occur earlier than 14 (\pm 4) days after vaccine 3, then no immune monitoring will be drawn at this additional leukapheresis. For subjects who complete all 10 study vaccines without progressing, an attempt will be made to obtain blood for immunologic monitoring 2-3 times a year at standard Duke neuro-oncology visits and at progression (whichever comes first). The immune monitoring blood that is collected prior to the initiation of post RT-TMZ cycle 1 (on the same day) will be the baseline for T_{reg} analysis. The immune monitoring blood drawn at pre-vaccine #1 will be the baseline for polyfunctional T cell analysis. The blood drawn on the same day as (but prior to) Td preconditioning will be analyzed for the baseline CCL3. A comparison of pre-therapy lymphocyte functions to those at intervals after each immunization will be made. These tests may provide evidence for the development of immune responses following DCs immunization and will play an important role in the design of future DC-based clinical trials. Cellular immune responses to pp65 will be measured by polyfunctional T cell assays using 10-12 color panels previously optimized in our laboratory, which includes detection of CCL3 on T cells. The effect of treatment on cytokines and other soluble factors will be assayed in the serum/plasma. Serum/plasma will be measured to determine levels of CCL3 from the blood drawn at the Td preconditioning visit, and at the vaccine #4 visit. T_{Reg} kinetics will be measured by using a constellation of markers specific for T_{Reg} s such as foxp3, CD25 and CD4. Whenever blood for immune monitoring is obtained, we will submit a CBC with auto differential to assess absolute number of T_{Reg} s. These will be drawn with SOC blood draws whenever possible.

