15.6.2 Secondary Objective #2: CCL3 and Survival

Objective	To assess the association between CCL3 measured post-Td administration and survival after vaccine # 4.
Analysis Set	All patients who undergo assessment of CCL3 after Td administration. All patients who reach vaccine 4 when Td is administered will be included in analyses. Forty (40) patients are anticipated.
Outcome	Survival from vaccine 4.
Hypothesis	Greater levels of CCL3 are associated with longer survival.
Analysis Plan	The Cox proportional hazards model will assess the impact of CCL3 on survival post-vaccine 4. The hazard ratio associate with a 1-unit increase in CCL3 will be estimated with 95% confidence intervals.
Power Analyses	Cox proportional hazards model will assess the impact of CCL3 on survival post-vaccine 4. Within ATTAC [129], the standard deviation for CCL3 was 12.9 and the hazard ratio for survival post-vaccine 4 was approximately 0.95 for a 1 unit increase in CCL3. Assuming SD=12.9, there would be 80% power to detect a hazard ratio of 0.95 with a two-tailed test ($\alpha=0.0167$) within a Cox model under these assumptions after 24 deaths [130, 131]. If we assume that the median OS post-vaccine 4 is 24 months, then 24 deaths should be observed approximately 20 months after the 40 th patient receives vaccine 4.

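### Section 15.7.1 tests an undefined CCL3 fold change against 0; on the ordinary post/pre meaning the no-effect value is 1, and only a log ratio makes the stated null sound

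*Combined protocol and SAP*

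**What the plan says.** Table 1 (Section 8) lists as an exploratory endpoint the "Mean fold change in CCL3 between pre- and post-Td pre-conditioning". The Additional Analyses row of Section 15.7.1 introduces the matching test with "As an additional exploratory analysis of CCL3". The method is "a one-sample t-test or a Wilcoxon rank sum test", and the test "will assess whether fold change in CCL3 between pre- and post-Td pre-conditioning differs from 0". No alpha, sidedness or power is given.

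Section 12.7.5 fixes the two measurements. For the first, "The blood drawn on the same day as (but prior to) Td preconditioning will be analyzed for the baseline CCL3". For the pair, "Serum/plasma will be measured to determine levels of CCL3 from the blood drawn at the Td preconditioning visit, and at the vaccine #4 visit".

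No section gives a formula for fold change. The Outcome row of 15.7.1 speaks of fold change, while its Analysis Plan row speaks of a change from before to after vaccine 4.

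The analysis set of 15.7.1 is patients with both a migration study and CCL3. Section 15.2 sets that at 16: "the first 16 patients who reach vaccine 4 will undergo migration analyses". Section 15.6.1 says the migration-survival analysis was dropped with protocol version 20220204, and Section 9.3 says the labelling study is no longer conducted. For CCL3 itself, Section 15.6.2 takes all patients who reach vaccine 4: "Forty (40) patients are anticipated".

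**The concern.** A null value has to fit the scale of the variable. For a ratio, no change is 1; for a log ratio or a relative change, it is 0. The plan names a variable that most readers will compute as a ratio and attaches the null of a difference. An analyst who follows the text literally would test whether a positive quantity differs from zero, which says nothing about Td.

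This is the only stated test of whether CCL3 moves across Td pre-conditioning. Section 12.7.5 gives that question as a purpose of the paired draws. With no control arm, the within-patient comparison is the only evidence on it, so a test that rejects under no effect would be reported as support for the mechanism.

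The named rank test is a separate slip. The rank sum test compares two independent groups, whereas this is one sample of within-patient changes. The Additional Analyses row of Section 15.6.3 has the same slip: it names the signed rank test for the paired comparison, then the rank sum test for fold changes at the second leukapheresis.

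**Working it through.** The plan gives no figure for this test, so there is nothing to reproduce. The check asks how often each reading rejects when Td has no effect.

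**Inputs.**
- From the documents: null value 0 and the test names (15.7.1); n up to 16 (15.2) or 40 (15.6.2).
- Assumed: two-sided 5%; the ratio R = post/pre lognormal with median 1; SD of log R from 0.3 to 1.0, with 2.0 as an extreme. The documents give no SD for this ratio.
- Median 1 is the natural form of no effect: if Td does nothing, the two draws are exchangeable and log R is symmetric about 0.

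**Step 1: signed rank test of R against 0.** Every R is positive, so all signs agree and the exact two-sided p is 2/2^n whatever the values. At n=16 it is 2/65,536 = 3.1e-5; at n=40 it is 1.8e-12. Since 2/2^6 = 0.031, it rejects for any n of 6 or more.

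**Step 2: t-test of R against 0.** The statistic is roughly √n divided by the coefficient of variation. With log-SD 0.4, CV = √(e^0.16 − 1) = 0.417, so t is about 4/0.417 = 9.6 at n=16, against a critical value of about 2.13. As the spread grows, a few very large ratios inflate the SD and the rejection rate falls.

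**Step 3: relative change against 0.** (post-pre)/pre equals R − 1, so this is the same as testing the mean of R against 1. But the mean of a lognormal with median 1 is e^(s²/2): 1.046 at s=0.3 (e^0.045) and 1.377 at s=0.8 (e^0.32). The t-test picks up that skew as an effect.

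**Step 4: log R against 0.** The null and the scale agree.

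Simulated rejection rates of the t-test with no Td effect (4,000 trials per row):

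| n | log-SD | R vs 0 | (post-pre)/pre vs 0 | log R vs 0 |
|---|---|---|---|---|
| 16 | 0.4 | 100% | 6.4% | 5.0% |
| 16 | 0.7 | 100% | 10.1% | 5.0% |
| 16 | 1.0 | 97.7% | 12.3% | 5.3% |
| 16 | 2.0 | 51.2% | 12.9% | 5.3% |
| 40 | 0.4 | 100% | 17.6% | 5.1% |
| 40 | 0.7 | 100% | 36.7% | 4.6% |
| 40 | 1.0 | 99.9% | 53.5% | 4.2% |
| 40 | 2.0 | 79.2% | 57.7% | 5.1% |

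Over log-SD 0.3 to 0.8, the relative-change t-test rejects about 6% to 11% at n=16 and 12% to 43% at n=40. The signed rank test on log R rejected 2.9% to 5.3% across all settings run (n = 12 to 40, log-SD 0.2 to 2.0).

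**Step 5: an illustration with a documented SD.** The only fold-change SD in the protocol is 1.589, for polyfunctionality (15.6.3). Borrowing it with a mean ratio of 1, the noncentrality is √n/1.589: 2.52 at n=16 and 3.98 at n=40. A normal-theory t-test against 0 then rejects about 65% and 97% of the time.

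**The case against.** The strongest reply is that post/pre is a reading, not a quotation. The plan gives no formula, and its choice of 0 is itself some evidence that a log ratio or a relative change was intended. This stands in part: if log(post/pre) was meant, the null is right and the fault is only that the scale is unstated. It does not rescue relative change, for which 0 is the matching value but the t-test is still inflated by skew.

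A reader might infer that the test will report an effect whatever the data show. That is true of the signed rank test on ratios. It is not true of the t-test, which the plan names first: with very wide spread it rejects only about half the time at n=16. The documents give no spread for CCL3 ratios, so near-certainty is conditional on the assumed range.

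A reader might also take n=40 as the relevant size. The section's own set is at most 16 migration patients, and possibly fewer now that the labelling has stopped. Forty applies only if the set is widened.

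Finally, a reader might infer that the secondary CCL3 objective rests on this test. It does not. The opening of Section 15.6 lists fold change in CCL3 among the predictors, but Table 1 and Section 15.6.2 model the post-Td CCL3 level against survival, and neither uses this comparison.

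**Conclusion.** As worded, the null value is paired with a variable for which it is sound only on one unstated definition, the log ratio. On the ordinary post/pre reading, and with no Td effect, the signed rank test against 0 always rejects at these sample sizes. The t-test rejects in about 97% to 100% of trials at n=16 for log-SD 0.3 to 1.0 and about 51% at log-SD 2.0. On the relative-change reading the error is smaller but real, and grows with n. These rates rest on lognormal ratios with median 1, an assumed spread and a two-sided 5% level; the signed rank result needs only positive ratios and that level. The rank sum test does not fit the one-sample question on any definition.

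The reach is limited. This is an exploratory add-on with no alpha or decision rule of its own. The documents do not support extending the problem to the primary endpoint or to the CCL3 survival model.

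**What to change.** In Section 15.7.1:
- Define CCL3 fold change as post-Td (vaccine 4 visit) divided by pre-Td (pre-conditioning visit, before Td).
- Test log(fold change) against 0 by one-sample t-test or Wilcoxon signed rank test, stating sidedness and alpha.
- Report the geometric mean fold change with a 95% CI, read against 1. Changing the null from 0 to 1 on the raw ratio would not be enough, because that is the relative-change test above.
- Run the analysis in all patients with both CCL3 draws, since the present set depends on migration studies that ended with version 20220204.

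Use the same definition in Table 1. In the Additional Analyses row of Section 15.6.3, replace the rank sum test with the signed rank test and state its null value.

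The cost is a few sentences of wording. Both draws are already in the schedule of events, so no new samples or visits are needed.
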